8.3.3.3. Assessment of outcomes

The investigator will assess the outcome of all unsolicited AEs (including SAEs) recorded during the study as:

- Recovered/resolved.
- Recovering/resolving.
- Not recovered/not resolved.
- Recovered with sequelae/resolved with sequelae.
- Fatal (SAEs only).

8.3.3.4. Medically attended visits

For each solicited and unsolicited symptom the subject experiences, the subject will be asked if he/she received medical attention defined as hospitalisation, or an otherwise unscheduled visit to or from medical personnel for any reason, including emergency room visits. This information will be recorded in the in the eCRF.

8.4. Reporting of serious adverse events, pregnancies, and other events**8.4.1. Prompt reporting of serious adverse events, pregnancies, and other events to GSK Biologicals**

SAEs that occur in the time period defined in Section 8.3 will be reported promptly to GSK within the timeframes described in Table 18, once the investigator determines that the event meets the protocol definition of a SAE.

Pregnancies that occur in the time period defined in Section 8.3 will be reported promptly to GSK within the timeframes described in Table 18, once the investigator becomes aware of the pregnancy.

pIMDs that occur in the time period defined in Section 8.3 will be reported promptly to GSK within the timeframes described in Table 18, once the investigator becomes aware of the pIMD.

Table 18 Timeframes for submitting serious adverse event, pregnancy and other events reports to GSK Biologicals

Type of Event	Initial Reports		Follow-up of Relevant Information on a Previous Report	
	Timeframe	Documents	Timeframe	Documents
SAEs	24 hours*	electronic SAE report	24 hours*	electronic SAE report
Pregnancies	2 weeks*	electronic pregnancy report	2 weeks*	electronic pregnancy report
pIMDs	24 hours**	electronic SAE report	24 hours*	electronic SAE report

* Timeframe allowed after receipt or awareness of the information.

**Timeframe allowed after the diagnosis is established and known to the investigator

8.4.2. Contact information for reporting serious adverse events and other events to GSK Biologicals

Back-up Study Contact for Reporting SAEs
24/24 hour and 7/7 day availability:
GSK Biologicals Clinical Safety & Pharmacovigilance Fax: + [REDACTED] or + [REDACTED]

8.4.3. Completion and transmission of SAE reports to GSK Biologicals

Once an investigator becomes aware that a SAE has occurred in a study subject, the investigator (or designate) must complete the information in the electronic SAE report

WITHIN 24 HOURS. The SAE report will always be completed as thoroughly as possible with all available details of the event. Even if the investigator does not have all information regarding a SAE, the report should still be completed within 24 hours. Once additional relevant information is received, the report should be updated WITHIN 24 HOURS.

The investigator will always provide an assessment of causality at the time of the initial report.

8.4.3.1. Back-up system in case the electronic SAE reporting system does not work

If the electronic SAE reporting system does not work, the investigator (or designate) must complete, then date and sign a paper SAE report and fax it to the GSK Biologicals Clinical Safety and Pharmacovigilance department within 24 hours.

This back-up system should only be used if the electronic SAE reporting system is not working and NOT if the system is slow. As soon as the electronic SAE reporting system is working again, the investigator (or designate) must complete the electronic SAE report within 24 hours. The final valid information for regulatory reporting will be the information reported through the electronic SAE reporting system.

8.4.4. Completion and transmission of pregnancy reports to GSK Biologicals

Once the investigator becomes aware that a subject is pregnant, the investigator (or designate) must complete the required information onto the electronic pregnancy report WITHIN 2 WEEKS.

Note: Conventionally, the estimated gestational age (EGA) of a pregnancy is dated from the first day of the last menstrual period (LMP) of the cycle in which a woman conceives. If the LMP is uncertain or unknown, dating of EGA and the estimated date of delivery (EDD) should be estimated by ultrasound examination and recorded in the pregnancy report.

8.4.5. Reporting of pIMDs to GSK Biologicals

Once onset of a new pIMD or exacerbation of a pre-existing pIMD is diagnosed (serious or non-serious) in a study subject, the investigator (or designate) must complete the information in the electronic SAE report WITHIN 24 HOURS after he/she becomes aware of the diagnosis. A field on the SAE report allows to specify that the event is a pIMD and whether it is serious or non serious. The SAE report will always be completed as thoroughly as possible with all available details of the event, in accordance with the pIMD standard questionnaire provided. Even if the investigator does not have all information regarding a pIMD, the report should still be completed within 24 hours. Once additional relevant information is received, the report should be updated WITHIN 24 HOURS.

The investigator will always provide an assessment of causality at the time of the initial report.

Refer to Section 8.4.3.1 for back-up system in case the electronic SAE reporting system does not work.

8.4.6. Updating of SAE, pregnancy, and pIMD information after freezing of the subject's eCRF

When additional SAE, pregnancy, or pIMD information is received after freezing of the subject's eCRF, new or updated information should be recorded on a paper report, with all changes signed and dated by the investigator. The updated report should be faxed to the GSK Biologicals Clinical Safety and Pharmacovigilance department or to the Study Contact for Reporting SAEs (refer to the Sponsor Information Sheet) within the designated reporting time frames specified in Table 18.

8.4.7. Regulatory reporting requirements for serious adverse events

The investigator will promptly report all SAEs to GSK in accordance with the procedures detailed in Section 8.4.1. GSK Biologicals has a legal responsibility to promptly notify, as appropriate, both the local regulatory authority and other regulatory agencies about the safety of a product under clinical investigation. Prompt notification of SAEs by the investigator to the Study Contact for Reporting SAEs is essential so that legal obligations and ethical responsibilities towards the safety of other subjects are met.

Investigator safety reports are prepared according to the current GSK policy and are forwarded to investigators as necessary. An investigator safety report is prepared for a SAE(s) that is both attributable to the investigational vaccine/product and unexpected. The purpose of the report is to fulfil specific regulatory and GCP requirements, regarding the product under investigation.

8.5. Follow-up of adverse events, serious adverse events, and pregnancies

8.5.1. Follow-up of adverse events and serious adverse events

8.5.1.1. Follow-up during the study

After the initial AE/SAE report, the investigator is required to proactively follow each subject and provide additional relevant information on the subject's condition to GSK Biologicals (within 24 hours for SAEs; refer to Table 18).

All SAEs and pIMDs (serious or non-serious) documented at a previous visit/contact and designated as not recovered/not resolved or recovering/resolving will be reviewed at subsequent visits/contacts until the end of the study.

All AEs documented at a previous visit/contact and designated as not recovered/not resolved or recovering/resolving will be reviewed at subsequent visits/contacts until 30 days after the last vaccination.

8.5.1.2. Follow-up after the subject is discharged from the study

The investigator will follow subjects:

- with SAEs, pIMDs (serious or non-serious), or subjects withdrawn from the study as a result of an AE, until the event has resolved, subsided, stabilised, disappeared, or until the event is otherwise explained, or the subject is lost to follow-up.

If the investigator receives additional relevant information on a previously reported SAE, he/she will provide this information to GSK Biologicals using a paper SAE and/or pregnancy report as applicable.

GSK Biologicals may request that the investigator performs or arranges the conduct of additional clinical examinations/tests and/or evaluations to elucidate as fully as possible the nature and/or causality of the AE or SAE. The investigator is obliged to assist. If a subject dies during participation in the study or during a recognised follow-up period, GSK Biologicals will be provided with any available post-mortem findings, including histopathology.

8.5.2. Follow-up of pregnancies

Pregnant subjects will be followed to determine the outcome of the pregnancy. At the end of the pregnancy, whether full-term or premature, information on the status of the mother and child will be forwarded to GSK Biologicals using the electronic pregnancy report and the SAE report if applicable. Generally, the follow-up period doesn't need to be longer than six to eight weeks after the estimated date of delivery.

Regardless of the reporting period for SAEs for this study, if the pregnancy outcome is a SAE, it should always be reported as SAE.

8.6. Treatment of adverse events

Treatment of any AE is at the sole discretion of the investigator and according to current good medical practice. Any medication administered for the treatment of an AE should be recorded in the subject's eCRF (refer to Section 6.6).

8.7. Subject card

Study subjects must be provided with the address and telephone number of the main contact for information about the clinical study.

The investigator (or designate) must therefore provide a "subject card" to each subject. In an emergency situation this card serves to inform the responsible attending physician that the subject is in a clinical study and that relevant information may be obtained by contacting the investigator.

Subjects must be instructed to keep subject cards in their possession at all times.

9. SUBJECT COMPLETION AND WITHDRAWAL

9.1. Subject completion

A subject who returns for the concluding visit/is available for the concluding contact foreseen in the protocol is considered to have completed the study.

9.2. Subject withdrawal

Withdrawals will not be replaced.

9.2.1. Subject withdrawal from the study

From an analysis perspective, a 'withdrawal' from the study refers to any subject who did not come back for the concluding visit/was not available for the concluding contact foreseen in the protocol.

All data collected until the date of withdrawal/last contact of the subject will be used for the analysis.

A subject is considered a 'withdrawal' from the study when no study procedure has occurred, no follow-up has been performed and no further information has been collected for this subject from the date of withdrawal/last contact.

Investigators will make an attempt to contact those subjects who do not return for scheduled visits or follow-up.

Information relative to the withdrawal will be documented in the eCRF. The investigator will document whether the decision to withdraw a subject from the study was made by the subject himself/herself, or by the investigator, as well as which of the following possible reasons was responsible for withdrawal:

- Serious adverse event.
- Non-serious adverse event.
- Protocol violation (specify).
- Consent withdrawal, not due to an adverse event*.
- Moved from the study area.
- Lost to follow-up.
- Other (specify).

*In case a subject is withdrawn from the study because he/she/the subject's parent(s) has withdrawn consent, the investigator will document the reason for withdrawal of consent, if specified by the subject, in the CRF.

Subjects who are withdrawn from the study because of SAEs/AEs must be clearly distinguished from subjects who are withdrawn for other reasons. Investigators will

follow subjects who are withdrawn from the study as result of a SAE/AE until resolution of the event (see Section 8.5.1.2).

9.2.2. Subject withdrawal from investigational vaccine

A 'withdrawal' from the investigational vaccine refers to any subject who does not receive the complete treatment, i.e. when no further planned dose is administered from the date of withdrawal. A subject withdrawn from the investigational vaccine may not necessarily be withdrawn from the study as further study procedures or follow-up may be performed (safety or immunogenicity) if planned in the study protocol.

Information relative to premature discontinuation of the investigational vaccine will be documented on the Vaccine Administration screen of the eCRF. The investigator will document whether the decision to discontinue further vaccination was made by the subject himself/herself, or by the investigator, as well as which of the following possible reasons was responsible for withdrawal:

- Serious adverse event.
- Non-serious adverse event.
- Other (specify).

10. STATISTICAL METHODS

10.1. Primary endpoints

- Anti-gE humoral immunogenicity.
 - Vaccine response for anti-gE humoral immunogenicity, as determined by enzyme-linked immunosorbent assay (ELISA), at Month 3.
- Occurrence of solicited local and general symptoms.
 - Occurrence, intensity and duration of each solicited local symptom within 7 days (Days 0-6) after each vaccination.
 - Occurrence, intensity, duration and relationship to vaccination of each solicited general symptom within 7 days (Day 0-6) after each vaccination.
- Occurrence of unsolicited adverse events.
 - Occurrence, intensity and relationship to vaccination of unsolicited AEs during 30 days (Days 0-29) after each vaccination, according to the Medical Dictionary for Regulatory Activities (MedDRA) classification.
- Occurrence of Serious Adverse Events (SAEs).
 - Occurrence and relationship to vaccination of all SAEs from first vaccination up to 30 days post last vaccination.

- Occurrence of AEs of specific interest.
 - Occurrence of any potential Immune Mediated Diseases (pIMDs) from first vaccination up to 30 days post last vaccination.

10.2. Secondary endpoint

- Anti-gE humoral immunogenicity in each of the following age ranges: 50-59 YOA, 60-69 YOA and ≥ 70 YOA.
 - Anti-gE antibody concentrations, as determined by ELISA, at Month 0 and Month 3.
- Occurrence of SAEs.
 - Occurrence and relationship to vaccination of all SAEs during the period starting after 30 days post last vaccination until study end.
 - Occurrence of SAEs considered by the investigator to be related to vaccination during the period starting after 30 days post last vaccination until study end.
- Occurrence of AEs of specific interest.
 - Occurrence of any pIMDs during the period starting after 30 days post last vaccination until study end.

10.3. Determination of sample size

A sample size of 84 evaluable subjects is needed to demonstrate the primary objectives of this study. Assuming 10% non-evaluable subjects, approximately 96 subjects will be enrolled:

- 84 subjects will be necessary to rule out the null hypothesis that the lower limit (LL) of the vaccine response of the treatment group is inferior to 60% with at least 97% power.

10.3.1. Assumptions and software

The following assumptions are made:

- Type I error: 0.025 (One-sided).
- No information is currently available on the immune response conferred by HZ/su vaccine in subjects with a previous episode of HZ therefore, we assume a conservative vaccine response rate of 80%.
- Null-hypothesis: The LL of the vaccine response of the treatment group is lower than 60%.
- Alternative hypothesis: The LL of the vaccine response of the treatment group is at least 60%.
- Criteria for superiority based on vaccine response rate evaluated at one month post Dose 2, the Lower Limit of the 95% CI of the LL is at least 60%.

- Sample size calculations were done using Pass 2005 (Power Analysis of One Proportion).

Table 19 shows an overview of the different assumptions and power calculations when 96 subjects are enrolled.

Table 19 Power calculations for a one-sided binomial test for Relevant Superiority

Power	N evaluable	Vaccine response		Significance level	
		Lower limit	Assumed	Alpha 1-Sided	Beta
0.8124	84	0.6	0.75	0.025	0.1876
0.9786	84	0.6	0.80	0.025	0.0214

10.4. Study cohorts/ data sets to be analysed

Three cohorts are defined for the purpose of the analysis:

- Total Vaccinated cohort (TVC)
- According To Protocol (ATP) cohort for analysis of safety
- ATP cohort for analysis of immunogenicity

10.4.1. Total vaccinated cohort

The Total Vaccinated cohort (TVC) will include all vaccinated subjects with respect to the vaccine actually administered.

- The TVC for analysis of immunogenicity will include vaccinated subjects for whom data related to immunogenicity endpoints are available.
- The TVC for analysis of safety will include all subjects with at least one vaccine administered.
- The TVC for analysis of reactogenicity will include all subjects with at least one vaccine administration documented.

10.4.2. According To Protocol cohort for analysis of safety (*Amended: 20 February 2014*)

The ATP cohort for analysis of safety will include all subjects:

- who have received at least one dose of study vaccine according to their random assignment;
- for whom administration site of study vaccine is known/*correct*;
- who have not received other vaccine forbidden in the protocol.

10.4.3. According To Protocol cohort for analysis of immunogenicity

The ATP cohort for analysis of immunogenicity will include all evaluable subjects from the ATP cohort for safety analysis:

- Who meet all eligibility criteria (refer to Sections 4.2 and 4.3).
- Who comply with the procedures and intervals defined in the protocol for the active phase (till Month 3) (refer to Table 7).
- Who do not meet any of the criteria for elimination from an ATP analysis during the active phase (till Month 3) as listed in Section 6.6.2,
- Who did not receive a product leading to elimination from an ATP analysis during the active phase (till Month 3) as listed in Section 6.6.2,
- Who did not present with a medical condition leading to elimination from an ATP analysis during the active phase (till Month 3) as listed Section 6.7,
- For whom data concerning immunogenicity endpoint measures are available during the active phase (till Month 3).

10.5. Derived and transformed data**10.5.1. Handling of missing data**

For a given subject and a given immunogenicity measurement, missing or non-evaluable measurements will not be replaced. Therefore, a subject will be excluded from an analysis if all measurements are missing or non-evaluable.

For the analysis of solicited symptoms, missing or non-evaluable measurements will not be replaced. Therefore, the analysis of the solicited symptoms based on the TVC will include only subjects/doses with documented safety data (i.e., symptom screen/sheet completed).

For the analysis of unsolicited AEs/SAEs/concomitant medication, all vaccinated subjects will be considered and subjects who did not report an event will be considered as subjects without an event.

10.5.2. Humoral immune response

- A seropositive subject is a subject whose anti-gE Ab concentration is greater than or equal to the cut-off value.
- The seropositivity rate is defined as the percentage of seropositive subjects.
- The VZV gE-specific humoral immune response is defined as the percentage of subjects who have at least:
 - a 4-fold increase in the anti-gE antibodies concentration as compared to the pre-vaccination anti-gE antibodies concentration, for subjects who are seropositive at baseline, or,

- a 4-fold increase in the anti-gE antibodies concentration as compared to the anti-gE antibodies cut-off value for seropositivity, for subjects who are seronegative at baseline.
- The GMCs calculations are performed by taking the anti-log of the mean of the log concentration transformations. For descriptive statistics only, Ab concentrations below the cut-off of the assay will be given an arbitrary value equal to half the cut-off for the purpose of GMC calculation.

10.6. Analysis of demographics

Demographic characteristics (age at first study vaccination in weeks or years and gender), vaccination history, cohort description, withdrawal status will be summarised by group using descriptive statistics:

- Frequency tables will be generated for categorical variable such as centre.
- Mean, median, standard deviation will be provided for continuous data such as age.

10.7. Analysis of immunogenicity

The primary analysis will be based on the ATP cohort for analysis of immunogenicity. If, in any vaccine group, the percentage of vaccinated subjects with serological results excluded from the ATP cohort for analysis of immunogenicity is 5% or more, a second analysis based on the TVC will be performed to complement the ATP analysis.

Inferential analysis:

- The gE vaccine response rate (with exact 95% CI) will be calculated:
The primary objective is met if the 95% lower limit of the gE vaccine response rate is at least 60%.

Descriptive analysis:

At each time point when a blood sample result is available:

- Seropositivity rates for anti-gE (with exact 95% CI) will be calculated;
- GMCs with 95% CI will be tabulated for anti-gE.
- The distribution of antibody concentrations for anti-gE will be displayed using reverse cumulative distribution curves.
- Depending on the distribution of time from the last HZ episode to enrolment in this study, a stratified exploratory analysis of immunogenicity may be conducted. Details will be provided in the SAP.

10.8. Analysis of safety

The primary analysis for safety will be based on the TVC. A second analysis based on this ATP cohort will be performed to complement the TVC analysis.

When appropriate, tabulations will be presented overall and by time of occurrence relative to last vaccination (e.g., using windows such as Days 0 – 6, Days 0 – 29 and more than 30 days post-vaccination).

The results for the analysis of safety will be tabulated as:

- The percentage of subjects with at least one local *solicited* AE (solicited and unsolicited), with at least one general *solicited* AE and with any *solicited* AE during the solicited 7-day follow-up period will be tabulated with exact 95% Confidence Intervals (CI) after each vaccine dose and overall; (*Amended: 20 February 2014*)
- The percentage of subjects reporting each individual solicited local and general AE during the solicited 7-day-follow-up period will be tabulated with exact 95% CI;
- For all solicited symptoms, the same tabulation will be performed for grade 3 solicited AEs and for solicited general AEs with relationship to vaccination;
- The proportion of subjects with at least one report of unsolicited AE classified by the Medical Dictionary for Regulatory Activities (MedDRA) Preferred Terms and reported up to 30 days after each vaccination will be tabulated with exact 95% CI;
- The same tabulation will be performed for grade 3 unsolicited AEs and for unsolicited AEs with a relationship to vaccination. The proportion of AEs resulting in a medically attended visit will also be tabulated;
- Total number/percentages of doses (per dose and overall) followed by AEs will be tabulated;
- Number of subjects with pIMDs as listed in Section 8.1.5.1 will be tabulated;
- SAEs and withdrawal due to AE(s) will be described in detail.
- Depending on the distribution of time from the last HZ episode to enrolment in this study, a stratified exploratory analysis of safety may be conducted. Details will be provided in the SAP.

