1.2.2. Rationale for the study design

Study ZOSTER-033 will be an open and single arm study to collect immunogenicity and reactogenicity/safety data in subjects ≥ 50 years of age who previously have had HZ. These data will be compared with the ones from subjects without HZ in other HZ/su trials.

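### Protocol Section 10.8 tabulates medically attended events as a share of AEs instead of a proportion of subjects, so the row does not give the risk per vaccinated subject

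*Protocol*

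**What the plan says.** Section 10.8 lists the safety tabulations, and the unit of analysis changes within the list:

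- Individual solicited AEs are per subject: "The percentage of subjects reporting each individual solicited local and general AE during the solicited 7-day-follow-up period", with exact 95% CI.
- Unsolicited AEs are per subject: "The proportion of subjects with at least one report of unsolicited AE classified by the Medical Dictionary for Regulatory Activities (MedDRA) Preferred Terms", with exact 95% CI.
- Grade 3 and related unsolicited AEs inherit the subject unit: "The same tabulation will be performed for grade 3 unsolicited AEs and for unsolicited AEs with a relationship to vaccination".
- The next sentence, in the same bullet, is per AE: "The proportion of AEs resulting in a medically attended visit will also be tabulated". It mentions no confidence interval and does not say which AEs it covers.
- The following bullet is per dose: "Total number/percentages of doses (per dose and overall) followed by AEs will be tabulated".

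Section 8.3.3.4 describes collection: "For each solicited and unsolicited symptom the subject experiences, the subject will be asked if he/she received medical attention". The information is thus held per symptom within subject, for solicited and unsolicited events alike. Section 1.2.2 says of the immunogenicity and safety data: "These data will be compared with the ones from subjects without HZ in other HZ/su trials".

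**The concern.** Medical attendance separates AEs with clinical consequence from trivial ones. The natural question is how many vaccinated subjects had an AE that needed medical attention, and the stated measure does not answer it, for three reasons.

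1. The denominator is itself a safety outcome. If the number of attended AEs stays the same and more unattended AEs are reported, the share goes down. A less well tolerated vaccine could show a lower figure.
2. Subjects can contribute several AEs. The share is the same whether the attended AEs are spread over many subjects or concentrated in a few.
3. The share depends on how completely AEs of any kind are reported. That weakens it for a comparison with other HZ/su trials, where reporting may differ.

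No other part of the protocol provides a subject-level medically attended rate. If Section 10.8 is followed as written, that rate will not appear in the report.

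**Working it through.** The protocol states no figure for medically attended AEs, so there is no planned number to reproduce. What can be checked is how the two measures behave.

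**Inputs.** N = 96 vaccinated subjects, the enrolment target in Section 4.1. All event counts below are assumptions.

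**Formulas.**
- AE-based share = attended AEs / all AEs.
- Subject-based rate = subjects with at least one attended AE / N, with Clopper-Pearson 95% CI.

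**Step 1: dependence on the AE total.** Assume 12 attended AEs in 10 subjects, and vary only the total number of AEs.

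| All AEs | AE-based share | Subject-based rate (95% CI) |
|---|---|---|
| 40 | 12/40 = 30% | 10/96 = 10.4% (5.1% to 18.3%) |
| 60 | 12/60 = 20% | 10.4% (same) |
| 120 | 12/120 = 10% | 10.4% (same) |
| 240 | 12/240 = 5% | 10.4% (same) |
| 480 | 12/480 = 2.5% | 10.4% (same) |

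Doubling the AE total from 60 to 120 halves the share, while the number of affected subjects does not change. The larger totals become more plausible if solicited symptoms are counted, and the sentence does not settle whether they are.

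**Step 2: clustering.** Assume 12 attended AEs out of 60, and vary how many subjects they fall in.

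| Subjects affected | AE-based share | Subject-based rate (95% CI) |
|---|---|---|
| 12 | 12/60 = 20% | 12/96 = 12.5% (6.6% to 20.8%) |
| 6 | 20% | 6/96 = 6.3% (2.3% to 13.1%) |
| 3 | 20% | 3/96 = 3.1% (0.6% to 8.9%) |

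The share cannot tell these situations apart, although the number of affected subjects differs fourfold (12 against 3).

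**Step 3: can the subject-based rate be produced?** Yes. Section 8.3.3.4 has medical attention recorded for every solicited and unsolicited symptom of each subject. Section 10.5.1 already sets the denominators: all vaccinated subjects for unsolicited AEs, and those with documented symptom data for solicited AEs.

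**The case against.** The strongest reply is that the sentence is loose wording. It shares a bullet with a subject-level tabulation and may have been meant as subjects with such an AE; a statistical analysis plan could confirm this. That is possible, but the written text names a different unit, and a clarification would need the same edit. It is also not a detail left open for later, because the protocol states a denominator.

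A second reply is that the share of AEs leading to medical attention is a legitimate description of how serious the reported events were, and that Section 10.8 already mixes units. Both statements are true. They justify keeping the share as a supplement, but not making it the only medically attended figure. The any-AE rows and the per-dose row would also reveal part of a rise in trivial AEs, so the share would not be read in isolation.

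Some stronger readings are tempting, and the protocol does not support them:

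- *An invalid binomial interval is planned.* The exact 95% CI is attached to the subject-level rows. The medically attended sentence announces none, so non-independence of AEs is a caution for anyone who adds an interval, not a planned error.
- *The co-primary safety objective is compromised.* Sections 10.1 and 10.2 do not list medical attendance among the primary or secondary endpoints. The listed endpoints cover solicited symptoms, unsolicited AEs, SAEs and pIMDs. The safety objective has no success criterion.
- *Every neighbouring row is per subject.* This holds for the preceding rows and the first half of the bullet. The following row is per dose.
- *A distortion of a given size is to be expected here.* The protocol gives no AE frequencies. The tables above show an arithmetic property only.
- *This row will be compared with other trials.* Section 1.2.2 speaks of the data in general and does not name this row.

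**Conclusion.** The point holds as a minor improvement to a descriptive table. As written, Section 10.8 gives a medically attended figure that varies with the total number of AEs and is blind to clustering within subjects. It therefore does not give the risk per vaccinated subject and is poorly suited to comparison across HZ/su trials.

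The size of the effect in this trial is unknown. On the assumed counts, the share runs from 30% down to 2.5% for the same 12 attended AEs in the same 10 subjects. The direction of the effect assumes that attended AEs stay fixed while other AEs increase.

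The immunogenicity test, the sample size and the success criterion are unaffected.

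**What to change.** Replace the sentence in Section 10.8 with wording such as: *For solicited and unsolicited AEs separately, the proportion of subjects with at least one medically attended AE will be tabulated with exact 95% CI.*

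Naming both classes matters. The present sentence says AEs without limit, and medical attention is recorded for both, so a replacement confined to unsolicited AEs would drop medically attended solicited AEs without notice. The AE-level count or share may remain as a supplementary line, without a binomial interval and with its denominator stated.

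The cost is one sentence and the matching table rows. The data are already collected per symptom, so no new field, visit or procedure is needed.
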